**Aim 2:** Collect preliminary data for the intervention (surveys, interviews and cortisol levels) to assess effectiveness of the intervention to improve youth mental and physical health (e.g., behavioral, social, emotional, and physical functioning).

*Sources of Materials.* Assessment measures will include the: 1) Adapted ACE Self-Reporting Screener (which will only be given pre-intervention to determine ACE scores of participants) 2) "Toolkit" of validated survey measures to assess academic, social, and emotional functioning of adolescents across multiple domains; 3) Teacher Perceptions of Student Wellness Pre- and Post-Surveys, 4) Cortisol levels before, during, and after the intervention period, 5) Collection of reflective journals from the group participants, and 6) Collection of secondary behavioral and academic data (grade averages in reading and math, attendance, and office referrals).

The "toolkit" of validated student pre and post surveys includes the following measures:

To assess academic functioning:

- Engagement (Simons-Morton & Crump, 2002)

- Class Absences and School Misbehavior (adapted from Kessler, 2001)

To assess emotional and social functioning:

- Depressive Symptoms (SMFQ) (Adrian Angold & Elizabeth J. Costello, 1987)
- Generalized Anxiety Disorder 7-item (GAD-7) scale (Spitzer et al., 2006)
- Loneliness (Hughes et al., 2004)
- Difficulties in Emotion Regulation Scale (Neumann et al., 2010)

Teacher Perceptions of Student Wellness Surveys (rated on a Likert Scale of 1-5) include questions before and after program implementation relating to academic, emotional, and social functioning as well. Examples of survey questions include items assessing individual students, such as whether they are “in control of their behavior (e.g., less reactive),” “can concentrate on work,” and “can deal appropriately with stress and anxiety (e.g., during test-taking or similar events).” Teachers will be given an incentive of \$25 in classroom supply money (funneled through school administration) for the completion of each pre and post survey for each of the student participants.

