To protect student privacy, the ACE screening instrument will only quantify how many adverse events the child has experienced, **not** which ones; quantifying ACE scores will help the researcher triangulate the data to determine program efficacy for students with high, moderate, and low ACE scores. School and district administration will have access to anonymous ACE scores for the purpose of collecting demographic information on the participant population. The remainder of the anonymous data collected will be analyzed and reviewed by the community advisory board; decisions regarding program improvement, future implementation, and modifications will be made by the advisory board as well.

For all participants, the primary behavioral health assessments will utilize descriptive statistics and paired t tests with regards to the validated “toolkit” survey of students to address academic, social, and emotional functioning of adolescents (including measures such as the Generalized Anxiety Disorder Scale and Patient Health Questionnaire for Depressive Symptomology) and a Teacher Perception of Student Wellness Survey to assess changes pre-and post-intervention. Descriptive statistics will be utilized with health outcomes to compare pre-and post-intervention cortisol levels. Any secondary academic outcomes will also be analyzed descriptively pre-and post-intervention, as improvement in academic performance may serve as a proxy for improved well-being (attendance records pre-, during, and post-intervention (absences and times arriving late to school), office referral data prior to, during, and post-intervention, and grade average data based on numerical averages in students’ reading and math courses pre- and post-intervention). Baseline data regarding participants’ exposure to childhood trauma as measured by the ACE Self-Reporting Screener will be gathered to determine any relationships between individual ACE scores and outcomes from intervention.

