To allow all who are interested to participate in the study, the focus of this project will primarily be to determine feasibility of the intervention; therefore, no control group will be utilized, and the focus of the feasibility trial will be to examine pre and post survey results and cortisol levels. Volunteers will participate in the intervention for 8 weeks. During the intervention phase, the participation goal for each student will be to attend 75% or more of the intervention sessions (attendance will be recorded by the yoga instructor).

After students volunteer for program participation, to establish a baseline for participants, students will be given the ACE screening instrument/ toolkit of pre-surveys and then begin the 8-week intervention. Students will be administered cortisol testing at the beginning of weeks 1 and 4 and the conclusion of week 8 during the intervention, each time prior to the yoga session, and they will complete the post surveys at the conclusion of week 8. At each of the three testing periods, students will provide a saliva sample to the school nurse or PI, to be deidentified (using a code key system) before analysis by the CAIRHE Translational Biomarkers Core Lab at MSU. Testing will use the Abcam (ab154996) cortisol in vitro competitive ELISA (Enzyme-Linked Immunosorbent Assay) kit designed for the accurate quantitative measurement of cortisol in saliva (sensitivity 0.12 ng/ml). Deidentified cortisol data will be returned to the PI for re-identification using the code key. Comparisons using paired t tests between pre and post-surveys will be utilized to determine program efficacy, and any changes in cortisol levels throughout the duration of the program will be analyzed to assess any trends and whether this is a useful measure for the next study phase.

**Aim 3:** Use the preliminary data to modify (as needed) year two of the study for expansion to middle level students and/or increasing the number of high school participants.

This study will utilize descriptive statistics for pre- and post-interventions and analysis of cortisol levels throughout the program to determine the efficacy the intervention.

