## **Statistical Analysis Plan**

Quantitative analyses between pre-intervention (T1) and post-intervention (T2) scores will be utilized for participants who completed the measures at both time points using a paired samples t-test or a Wilcoxon signed rank test with continuity correction for non-normal distributions.

Next, analyses of covariance (ANCOVA) following treatment completion will be used to evaluate whether there are significant post-treatment differences in student-reported symptoms between children with low (0-1), moderate (2-3), and high (4+) ACE scores, with pre-intervention student-reported symptoms and attendance rate as the covariate. The outcome measures to be used in these analyses are the GAD-7, PHQ-A, SDQ, and the SDQ subscales. ANCOVA is the clearest and most straightforward analysis to address each of the analytic goals.

Salivary cortisol samples will be deidentified (using a code key system) before analysis by the CAIRHE Translational Biomarkers Core Lab at Montana State University. Testing utilized the Abcam (ab154996) cortisol in vitro competitive ELISA (Enzyme-Linked Immunosorbent Assay) kit designed for the accurate quantitative measurement of cortisol in saliva (sensitivity 0.12 ng/ml). Comparisons using paired t tests between pre and post-surveys will be utilized to determine program efficacy, and any changes in cortisol levels pre and mid-intervention were analyzed to assess any trends and aided in the decision-making process for whether to continue using this measure for the next study phase.

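### Efficacy is to be judged from several unadjusted tests with no stated alpha and no single primary outcome, so the chance of a false positive is several times that of one test

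*Combined protocol and SAP*

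**What the plan says.** Methods, Aim 2, states the purpose of the survey tests: "Comparisons using paired t tests between pre and post-surveys will be utilized to determine program efficacy". The SAP repeats the sentence. The SAP's pre/post comparison is made "using a paired samples t-test or a Wilcoxon signed rank test with continuity correction for non-normal distributions", in students who completed both time points.

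The SAP then adds a second family of tests: "Next, analyses of covariance (ANCOVA) following treatment completion will be used to evaluate whether there are significant post-treatment differences in student-reported symptoms" between low, moderate and high ACE bands, adjusting for the baseline score and attendance. Its outcome sentence reads: "The outcome measures to be used in these analyses are the GAD-7, PHQ-A, SDQ, and the SDQ subscales". The number of SDQ subscales is not given. Methods, Aim 2, also links ACE scores to efficacy, since they are meant to help "determine program efficacy for students with high, moderate, and low ACE scores".

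The protocol's own student battery, introduced as a set "of validated student pre and post surveys includes the following measures", has six lines: engagement; absences and misbehaviour; SMFQ; GAD-7; loneliness; emotion regulation. Only the GAD-7 is also on the SAP list. A teacher survey is tested pre/post as well. The word primary is applied to the student battery and the teacher survey together, not to one outcome. Cortisol and academic outcomes are mainly descriptive. Neither document states an alpha, an adjustment or an order of testing.

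**The concern.** When several outcomes are each tested at the usual level and any of them may support a statement of efficacy, the chance that at least one is significant by accident exceeds the level of a single test. This is separate from the lack of a control group: it remains even if there is no time trend and no regression to the mean.

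Aim 3 uses the preliminary data to modify and possibly expand the programme in year two, and an advisory board decides on future implementation. One isolated significant scale could reach that decision described as efficacy. The mismatch between the protocol's battery and the SAP's list widens the choice of which scale to put forward.

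**Working it through.** The plan gives no test count, alpha or family-wise error rate, so there is no figure to reproduce.

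**Inputs**
- Outcomes, from the SAP list: GAD-7, PHQ-A, SDQ total and the SDQ subscales. The plural means at least 2 subscales, so 3 + 2 = 5 outcomes. With five subscales (assumed; not in the documents), 3 + 5 = 8.
- Tests: one paired test and one ANCOVA per outcome, so 5 + 5 = 10 or 8 + 8 = 16. This reads the SAP's outcome sentence as covering both families.
- Alpha: not stated; two-sided 0.05 per test assumed.
- Sample size: 30 (Methods).
- Correlation between outcomes: not stated; 0 to 0.7 assumed.

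**Independent tests:** chance of at least one false positive = 1 − (1 − α)^m.
- 5 paired: 1 − 0.95^5 = 22.6%
- 8 paired: 1 − 0.95^8 = 33.7%
- 10 tests: 1 − 0.95^10 = 40.1%
- 16 tests: 1 − 0.95^16 = 56.0%

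**Favourable direction only.** Half of the two-sided rejections under the null are in the direction of worsening, so the rate per test is 2.5%.
- 5 paired: 1 − 0.975^5 = 11.9%
- 8 paired: 1 − 0.975^8 = 18.3%

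**Correlated outcomes.** Simulation under no change and no ACE effect: 30 students, three ACE bands of 10, baseline-to-post correlation 0.7, paired t tests, and ANCOVAs adjusting for baseline and attendance. The paired tests and ANCOVAs were simulated as the different tests they are, not as one equally correlated set.

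| Correlation | 5 paired | 5 + 5 | 5 favourable | 8 paired | 8 + 8 | 8 favourable |
|---|---|---|---|---|---|---|
| 0 | 23% | 40% | 12% | 34% | 56% | 18% |
| 0.5 | 18% | 35% | 9% | 25% | 45% | 13% |
| 0.7 | 15% | 28–29% | 7–8% | 19–20% | 36% | 10% |

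Making the SDQ total the sum of its subscales lowers the 8 + 8 figure slightly, to about 41% at correlation 0.5 and 34% at 0.7.

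**Sensitivity to alpha** (independent tests)
- α = 0.01: 9.6% for 10 tests, 14.9% for 16
- α = 0.10: 65.1% for 10 tests, 81.5% for 16

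**Pooling both outcome lists.** With two subscales, the six protocol lines, four further SAP measures and one teacher survey make 11 paired tests. Adding 5 ANCOVAs gives 16. The two lists conflict, so this is not a firm count.

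**The case against.** The strongest defence is context. Methods, Aim 2, says the project is primarily about feasibility and calls its data preliminary. Under Aim 1, possible expansion to the middle school rests on retention and satisfaction. No rule makes a decision turn on one significant scale, and leaving cortisol and academic outcomes mainly descriptive is a partial hierarchy. This lowers the weight of the point but does not remove it. Nowhere does the plan call the tests exploratory; it says that they settle efficacy.

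Four stronger readings are tempting, and the documents do not support them.
- **A reader might infer at least 16 tests.** That needs five SDQ subscales, an outside figure, or the pooling of two conflicting lists. The SAP text supports 10.
- **A reader might infer that a false positive is likely.** At 5% per test, independent tests pass 50% only from 14 tests on. These are related scales from the same students, and with 16 tests the figure falls to about 45% at correlation 0.5 and 36% at 0.7.
- **A reader might take the whole family-wise figure as the chance of a false efficacy claim.** The efficacy sentence names only the paired tests, an ACE-band difference does not show that the programme works, and a significant worsening would not be read as success. The favourable-direction figures are the relevant ones.
- **A reader might conclude that the documents already single out the GAD-7.** It can be traced through the protocol's battery, its analysis paragraph and the SAP, but under differing names, and nothing gives it priority. The plan also describes the intervention as academic rather than clinical, so the choice is open.

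**Conclusion.** The point holds in moderate form. The plan draws an efficacy conclusion from 5 to 8 unadjusted paired tests (SAP list) and adds as many unadjusted ANCOVAs, with no alpha and no single primary outcome.

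At an assumed two-sided 5%, for correlations from 0.7 down to 0, the chance of at least one false positive is:
- **Paired tests:** about 15–23% (5 outcomes) or 19–34% (8 outcomes).
- **With the ANCOVAs:** about 29–40% or 36–56%.
- **Favourable pre/post results only:** about 7–12% or 10–18%, against a nominal 2.5%.

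The 8-outcome figures depend on five SDQ subscales, and all of them depend on the assumed alpha. Even the lowest favourable figure is nearly three times nominal (7 / 2.5 = 2.8). The feasibility aim limits the consequences but does not justify the efficacy wording.

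**What to change.** In the SAP, and in the matching sentence of Methods, Aim 2, replace the efficacy statement with the following:
- At most one pre/post outcome, chosen by the investigators before the outcome data are examined, carries an inferential statement, at a stated alpha. The GAD-7 is a candidate because it can be followed through both documents.
- All other pre/post changes and all ACE-band contrasts are reported as estimates with 95% intervals, labelled exploratory.
- If p-values for those results are used to claim an effect, Holm is applied across that set. With 15 remaining tests (16 − 1), the smallest p-value is compared with 0.05 / 15 = 0.0033.
- If outcome data have already been examined, all tests are labelled exploratory. The SAP's past tense about the cortisol results suggests that some data had been seen.

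A single pre-specified test brings the error rate of the inferential statement back to 5%. The change is one of wording and needs no further students, visits or assays. The cost is that fewer results can be called significant.

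### The ACE-band ANCOVA estimates change in no band; report change by band beside it, and do not read the ANCOVA alone as differential benefit

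*Combined protocol and SAP*

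**What the plan says.** The Methods (Aim 2) explain that ACE scores are collected "to determine program efficacy for students with high, moderate, and low ACE scores". The screener is one "which will only be given pre-intervention to determine ACE scores of participants", so the bands are characteristics that students bring with them, not groups formed by randomisation. The same section states that "no control group will be utilized, and the focus of the feasibility trial will be to examine pre and post survey results and cortisol levels".

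Both the Methods (Aim 2) and the Statistical Analysis Plan say that programme efficacy will be determined by paired t tests of pre against post surveys. That measures efficacy as mean within-student change.

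For the ACE comparison, the SAP plans an ANCOVA to "evaluate whether there are significant post-treatment differences in student-reported symptoms between children with low (0-1), moderate (2-3), and high (4+) ACE scores". The model adjusts for each student's baseline score and for attendance. On outcomes it says: "The outcome measures to be used in these analyses are the GAD-7, PHQ-A, SDQ, and the SDQ subscales". The reason given for the method is that "ANCOVA is the clearest and most straightforward analysis to address each of the analytic goals". No analysis of change by ACE band is planned. The documents give no expected baseline difference between bands, no pre-post correlation and no band sizes.

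**The concern.** Efficacy overall is defined through change, and efficacy by ACE level is a stated purpose, but the one ACE analysis estimates something else: the difference in post-scores between bands among students with the same baseline score. Bands that are not randomised may differ at baseline. When they do, the adjusted post-score difference and the difference in change are different quantities and can point in different directions.

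What is at stake is interpretation. If high-ACE students begin with more symptoms and every band improves equally, the ANCOVA will tend to show the high band worse after treatment. A reader who takes that as the answer on efficacy by ACE level would conclude that these students benefited less. The outcomes would tend to lean the same way wherever the high band starts worse, so the pattern could look like consistent evidence.

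**Working it through.** The documents give no figure for this comparison, so there is none to reproduce.

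**Inputs from the documents.** 30 students in total; three ACE bands; model of post-score on baseline score, attendance and band; no control group.

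**Assumptions, not in the documents.** Higher score means more symptoms; within-band SD of 1 at both times, so the within-band slope equals the correlation rho; high band D SD above low at baseline, moderate midway; 10 students per band (15/9/6 also tried); no dropout; attendance unrelated to outcome; two-sided alpha 0.05.

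**Step 1: how the two contrasts relate.** Let P be the high-minus-low difference in mean post-score.

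- ANCOVA contrast: A = P - rho × D
- Change contrast: C = P - D
- Hence A - C = (1 - rho)D

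The two agree only if D = 0 or rho = 1.

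**Step 2: equal change in every band.** Then P = D and C = 0, so A = (1 - rho)D.

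| D | rho = 0.5 | rho = 0.7 | rho = 0.9 |
|---|---|---|---|
| 0.5 | 0.25 | 0.15 | 0.05 |
| 1.0 | 0.50 | 0.30 | 0.10 |
| 1.5 | 0.75 | 0.45 | 0.15 |

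Simulating the SAP model (2,000 runs per setting, 10 per band, 2-df test of band) gives these rejection rates at rho 0.5 / 0.7 / 0.9:

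- D = 0: 4 to 5%
- D = 1.0: 15% / 12% / 6%
- D = 1.5: 25% / 14% / 8%

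For D = 0.5, a simulation without attendance in the model gives only 6 to 8% (rho 0.5 to 0.8). With bands of 15/9/6 and D = 1.0 the rates are 13% / 10% / 6%. At 10 per band the point estimate goes against the high band in 60 to 94% of runs for D from 0.5 to 1.5. The change-score test stays at 4 to 6% throughout. With 100 per band and D = 1.0 (600 runs), the ANCOVA rejects in 93% / 69% / 27%, so a larger sample does not remove the difference.

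**Step 3: the opposite truth, no band difference at the same baseline score.** Then P = rho × D and A = 0, so C = -(1 - rho)D. At D = 1.0 and 10 per band the simulated change contrast is -0.50 / -0.30 / -0.10 SD, with rejection in 12% / 11% / 8% of runs. The ANCOVA stays near zero, with rejection close to 5%. Here it is the change contrast that would mislead, making the high band look as if it benefited more.

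**Step 4: precision.** At rho = 0.5 the SD of change is sqrt(2 - 2 × 0.5) = 1.00, against an ANCOVA residual SD of sqrt(1 - 0.5²) = 0.87. With 10 students in a band, a 95% interval for mean change is about ±2.262 × 1.00/sqrt(10) = ±0.72 SD.

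**The case against.** The strongest reply is that the SAP asks its own question and answers it correctly. It specifies post-treatment differences with baseline as a covariate, which is a comparison at equal baseline score, and ANCOVA is valid for that. The Methods do not define a difference-in-change estimand; they also speak more loosely of relationships between ACE scores and outcomes. Step 3 shows that a change contrast has the mirror-image problem. This stands, and it is why change scores should not replace the ANCOVA.

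A second reply is that the change contrast is not guaranteed to centre on zero even when the programme works equally in all bands. That also requires equal natural course and equal regression to the mean. Students put forward by school administrators are offered places first, then volunteers, so selection related to current symptoms cannot be excluded. As an assumed illustration, take population band means of 0 and 1 SD, enrolment only above 1 SD, rho = 0.5 and no programme effect. Enrolled students then sit on average 1.525 SD (low) and 0.798 SD (high) above their own band means, so the change contrast is 0.5 × (1.525 - 0.798) = 0.36 SD. The ANCOVA contrast is 0.50 SD. Neither is zero. This stands too.

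A reader might infer that high-ACE students will appear to benefit less, or that the ANCOVA is simply biased. The documents do not support either: they give no baseline gap and no slope, and a significant false difference is a minority result at 30 students. Nor do they support a claim that the result would steer targeting by ACE band in year two. Aim 3 concerns extension to middle-level students or more high-school participants.

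What the replies do not remove is that the planned analysis provides no change estimate for any ACE band, although the documents judge efficacy by change and want it by ACE level.

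**Conclusion.** The point holds as a mismatch between the stated purpose and the planned analysis. The adjusted contrast is legitimate for equality at the same baseline score, but it does not by itself show efficacy within ACE bands or differential benefit between them, and the SAP's general justification hides this. The possible misreading has size (1 - rho)D under equal change: 0.05 to 0.75 SD over D of 0.5 to 1.5 and rho of 0.5 to 0.9, and zero if the bands start level. Every one of these values rests on an assumed D and rho. With no control group, neither contrast separates differential benefit from natural course or regression to the mean. This is a cheap improvement in an uncontrolled feasibility study, not a reason to abandon the ANCOVA.

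**What to change.** In the Statistical Analysis Plan:

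1. For each ACE band, report the number of students, mean pre-to-post change and its 95% interval, and report the between-band difference in change with its interval, beside the planned ANCOVA.
2. State that the ANCOVA compares post-scores at the same baseline score and is not by itself evidence of differential benefit.
3. Label both comparisons exploratory and give the reason: there is no control group.
4. Remove the sentence claiming that ANCOVA serves every analytic goal.

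The cost is one extra table, built from pre and post scores that the ANCOVA already needs, and a few lines of text. The change contrast is somewhat less precise, the band intervals will be wide, and the two contrasts may disagree. The text should say in advance that disagreement is expected when bands differ at baseline, and should show the baseline means by band so that a reader can see why.

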It is possible that the intervention may bring up strong emotions for the participants; so too might the administration of the ACE survey which will be part of the preliminary data collection (more below). To mitigate this potential, the PI will caution students that this may occur and emphasize the importance of self-care and knowing one's own limits with the intervention. Immediate referrals regarding suicidality, self-harm, depressive thoughts, etc. will be directed to the school nurse. If needed, referrals for additional, outside treatment will be provided as determined by school officials and/or requested by the participant and/or the participant's legal guardian(s). It will also be explained to participants that this study is not designed to be a clinical/psychological intervention but rather an academic intervention, so students that need additional mental health supports will be referred to appropriate outside agencies.

Additional resources for outside assistance will be shared with participants and participant parents/guardians on the assent/consent forms, listing the following avenues for additional help:

- Talking with someone who you can trust
- Calling 911, your doctor or other healthcare provider
- Going to an Emergency Room
- Calling [name] to talk with a crisis worker for free
- Texting 741741 to text with a counselor for free

Visiting NowMattersNow.org to learn skills for dealing with thoughts of suicide

**Aim 1:** Foster a partnership with a rural southwestern Montana school and test the feasibility of implementing a trauma-informed yoga intervention.

For this pilot study, feedback will be gathered from the school district, teachers, and students from the focus group via conversations and/or email communications to determine the level of burden from the various assessment instruments and participation in the pilot; plans and identified needs for this study are ongoing with the school district and the PI. Retention and satisfaction of participants, as measured by survey instrumentation) from year one will indicate the feasibility of an ongoing partnership with the school district, determine possible expansion to the middle school in year two, and will assess both students' and teachers' perception of value of the intervention. Because this is a feasibility study, no control group will be utilized, and the focus of the project will be to examine pre and post survey results and cortisol levels.

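### The plan says uncontrolled pre-post comparisons will determine efficacy; the single-group feasibility design supports only a statement about change

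*Combined protocol and SAP*

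**What the plan says.** **Design.** Methods, Aim 1: "Because this is a feasibility study, no control group will be utilized". The later Aim 2 text gives feasibility as the project's primary purpose and says "therefore, no control group will be utilized".

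**Stated inference.**
- The Statistical Analysis Plan, and the same sentence in Methods under Aim 2, says "Comparisons using paired t tests between pre and post-surveys will be utilized to determine program efficacy".
- Methods, Aim 3, names descriptive statistics and "analysis of cortisol levels throughout the program to determine the efficacy the intervention".
- Methods, Aim 2, on the ACE screener, speaks of using the scores to "determine program efficacy for students with high, moderate, and low ACE scores".
- The Aim 2 statement itself is softer. It collects preliminary data "to assess effectiveness of the intervention to improve youth mental and physical health".

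**Planned analyses.** The SAP compares pre- and post-intervention scores among students with both measurements, "using a paired samples t-test or a Wilcoxon signed rank test with continuity correction for non-normal distributions". It then plans an ANCOVA of post-treatment symptoms between low, moderate and high ACE groups, adjusted for the pre-intervention score and attendance rate. Elsewhere in Methods the survey analyses, including the paired tests, are described more modestly, as being "to assess changes pre-and post-intervention".

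**The concern.** The plan justifies having no control group by the feasibility purpose, then claims an inference that needs one. The null hypothesis of a paired test is no mean change between two dates. It is not that the program has no effect. The two coincide only if scores would have stayed still without the program, and the plan gives no reason to assume that.

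Several things other than yoga could move the scores: the point in the school year, answering the same questionnaire twice, self- and teacher-ratings made by people who know the program took place, and restriction to students who completed both surveys. The first two are general considerations that the documents do not discuss.

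What is at stake is the conclusion. As written, a significant pre-post change could be reported as efficacy, and a flat result as lack of efficacy. Neither would follow.

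**Working it through.** The plan gives no power calculation, alpha, effect size, SD or correlation, so there is no figure of its own to reproduce. The point rests on the text; the arithmetic only shows scale.

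**1. Does any planned analysis separate program effect from change over time?**
- Paired t or Wilcoxon test: each student against his or her own baseline, with no untreated comparison.
- ANCOVA: compares ACE strata, all of which receive the program. It can show whether adjusted post scores differ between strata, not whether the program worked in any of them.
- Cortisol at weeks 1, 4 and 8: all samples fall within the intervention period in the same group.
- Repeated baseline, external control or waiting-list group: none described.

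So the answer is no. No sentence withdraws or limits the efficacy wording either.

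**2. How far can change and effect diverge?**

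Inputs: n = 30 is the planned enrolment (Methods). Assumed, not in the documents: two-sided alpha 0.05; equal SD before and after; pre-post correlation ρ of 0.5 or 0.8; one scale; t test only. The 21 completers (70% of 30) are also an assumption, used to show dropout.

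- SD of change = √(2(1−ρ)) SD: 1.000 at ρ = 0.5 and 0.632 at ρ = 0.8.
- Standardized change d_z = shift ÷ SD of change.
- P(significant improvement) = P(T > t₀.₉₇₅,ₙ₋₁), where T is noncentral t with noncentrality d_z√n. The critical value is 2.045 for n = 30 and 2.086 for n = 21.

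Worked case: shift 0.2 SD, ρ = 0.8, n = 30. d_z = 0.2 ÷ 0.632 = 0.316; noncentrality = 0.316 × √30 = 1.732; probability 0.388.

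Program effect zero, 30 completers:

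| Background shift | ρ = 0.5 | ρ = 0.8 |
|---|---|---|
| 0.1 SD worsening | 0.6% | 0.3% |
| none | 2.5% | 2.5% |
| 0.1 SD improvement | 7.6% | 13.1% |
| 0.2 SD improvement | 18.4% | 38.8% |

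The error also runs the other way. A real benefit of 0.3 SD is detected in 36-71% of studies with no drift, but in 18-39% if the background worsens by 0.1 SD (net shift 0.3 − 0.1 = 0.2 SD).

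**3. What can the study estimate?** Mean change, with 95% CI half-width t₀.₉₇₅,ₙ₋₁ × SD of change ÷ √n:
- n = 30: 2.045 × 1.000 ÷ 5.477 = 0.37 SD (ρ = 0.5); 2.045 × 0.632 ÷ 5.477 = 0.24 SD (ρ = 0.8).
- n = 21: 2.086 × 1.000 ÷ 4.583 = 0.46 SD (ρ = 0.5); 2.086 × 0.632 ÷ 4.583 = 0.29 SD (ρ = 0.8).

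At 21 completers, detection of a 0.3 SD benefit without drift falls to 26-54%. For precision and power, 30 completers is therefore the best case.

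**The case against.** The best defense is that this is openly a pilot. Feasibility is given as the primary purpose and as the reason for having no control; Aim 2 speaks of preliminary data; Aim 3 uses the results to adjust year two; possible middle-school expansion is tied to retention and satisfaction; and program decisions belong to the advisory board. No sample size, test or formal decision depends on the efficacy wording. All of that stands, and it lowers the weight of the point. It does not remove it: the efficacy claim appears in the SAP, is repeated in Methods, and is never qualified.

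It is also fair that alpha, correlation and drift above are assumptions, that 30 completers means no dropout, and that the Wilcoxon alternative is not covered. The figures show scale only.

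A reader might infer more than the documents support:
- *That the design or the tests are wrong.* A single group with paired tests is acceptable for feasibility work.
- *That the results will be biased toward benefit.* Administrator-recommended students are offered slots first, which suggests regression to the mean. But no criteria are given and nothing says these students start with elevated symptoms. The net direction is unknown.
- *That Aim 2 must be rewritten.* It is already labelled preliminary and speaks of assessing, not determining.
- *That retention, satisfaction and attendance should become the main results.* Methods puts the focus on pre-post surveys and cortisol and calls the survey-based assessments primary. Reordering would create a new contradiction.

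**Conclusion.** The point holds, and it concerns the stated conclusion only. The efficacy sentence in Methods and the SAP, and the matching Aim 3 sentence, claim what a single-group pre-post comparison cannot deliver; the ACE-stratum phrase has the same fault. This follows from the text and needs no assumption.

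It should be fixed, but the consequence is modest: it affects what a report may claim, not a formal decision. Under the assumptions shown, 0.1-0.2 SD of background improvement would raise the chance of a significant improvement on one scale, with no program effect, from 2.5% to between 8% and 39%. Background worsening could equally hide a real benefit. The paired tests cannot tell these cases apart.

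**What to change.** 1. **Survey sentence in the SAP and in Methods, Aim 2.** Replace the closing statement of purpose in "Comparisons using paired t tests between pre and post-surveys will be utilized to determine program efficacy" with: *to estimate within-student pre-post change, reported with 95% CIs (mean change, or a Hodges-Lehmann estimate where the Wilcoxon test is used); without a control group, no efficacy conclusion will be drawn*. Let the cortisol clause that follows stand as its own sentence.
2. **Methods, Aim 3.** Replace the purpose stated at the end of "analysis of cortisol levels throughout the program to determine the efficacy the intervention" with: *to describe pre-post change and cortisol levels over the program; no efficacy conclusion will be drawn*.
3. **Methods, Aim 2, ACE screener.** Replace "determine program efficacy for students with high, moderate, and low ACE scores" with wording that matches the SAP's ANCOVA, such as: *explore whether post-intervention scores, adjusted for baseline and attendance rate, differ between ACE strata*.

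The Aim 2 statement and the ordering of outcomes stay as they are.

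**Cost.** Wording in Methods and the SAP, plus confidence intervals from data already planned. No test, sample or visit changes. The SAP's past tense on cortisol suggests that some of those data may already have been examined; limiting the conclusion is still possible in that case. The downside is a more modest stated conclusion.
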